10.2.2 Reasons Leading to the Exclusion from an Analysis Set

Not applicable.

11 Demographics and Other Baseline Characteristics

If not stated otherwise, the following analyses will be performed based on the FAS per indication or per parent protocol of the corresponding parent study.

11.1 Demographics

Demographic characteristics will be summarized descriptively using the following information from the parent study Baseline Visit eCRF pages.

The following demographic characteristics will be included:

- Sex: male, female,
- Race: American Indian or Alaska Native, Asian, Black or African American, Native Hawaiian or Other Pacific Islander, White, More than one race, Other, Not collected at this site
- Ethnicity: Hispanic or Latino/Not Hispanic or Latino
- Ethnicity: Japanese/Not Japanese
- Age (years) at parent study consent
- Age categories at parent study consent:
 - < 65 years,
 - ≥ 65 years
 - 65- < 75,
 - 75- < 85,
 - ≥85 years

- Pooled Region (as applicable):

North America

Europe

Asia

Rest of the World

- Geographic Region:

North America

Latin America

Western Europe

Eastern Europe

Middle East

Australia

Asia

11.2 Medical History

The medical history will not be presented in table or listing, although the SDTM data is available.

11.3 Other Baseline Characteristics

Information on disease characteristics collected at parent study baseline will be summarized. Summary statistics will, if applicable, be presented for:

- Primary site of tumor,
- Time since initial disease diagnosis (in months) to parent study baseline,
- Tumor, Node and Metastasis (TNM) classification at initial diagnosis,
- TNM classification at parent study baseline,
- Histopathological classification (clear cell, sarcomatoid, other)

12 Concomitant Therapies/Procedures

The following analyses will be performed based on the Full Analysis Set per indication or per parent protocol of the corresponding parent study.

Concomitant medications are medications, other than study intervention, which are taken by participants any time during the on-treatment period, see Section 9.7.

Concomitant medication will be summarized by number and percentage of participants from the “Concomitant medications and/or Procedures” eCRF. Preferred term within ATC classification

code level 2 will be tabulated as given from the WHO-DD dictionary most current version at time of study database lock.

If concomitant medication is classified into multiple ATC classes, the medication will be summarized separately under each of these ATC classes.

The summary tables will be sorted by decreasing frequency of drug class and decreasing frequency of preferred term in each drug class. In case of equal frequency regarding ATC classification level 2 or preferred term, alphabetical order will be used.

In case any specific medication does not have an ATC classification level 2 coded term, it will be summarized under “Unavailable ATC classification” category. Each participant will only be counted once, even if he/she received the same medication at different times.

A listing of concomitant medications will be created with the relevant information collected on the “Concomitant Medications Details” eCRF page.

All **concomitant procedures**, which were undertaken during the on-treatment period will be summarized in a listing according to the information collected on the CRF page “Concurrent Procedures”.

Subsequent anti-cancer therapy

Anti-cancer treatment after discontinuation will be provided in a listing with data retrieved from the “Anti-Cancer Treatment After Discontinuation Details”, “Radiotherapy After Discontinuation Details”, and “Surgery After Discontinuation Details” eCRF pages.

13 Study Intervention: Compliance and Exposure

The exposure duration (in weeks) of study intervention since first administration of study interventions in the parent study will be calculated based on the safety analysis set per indication or per parent protocol of the corresponding parent study. The detail on the calculation of exposure duration is described in Section 9.8.

14 Efficacy Analyses

The following analyses will be performed based on the FAS and presented as listings.

14.1 Secondary Endpoints

14.1.1 Secondary Objective: Analysis of the secondary endpoints

The below analysis will be performed per indication or parent protocol of the corresponding parent study cohort if there are at least 5 subjects enrolled per indication or parent protocol of the corresponding parent study cohort. Listings of the time-to-events will be presented.

Analysis (AnalysisSet)	Derivation	Statistical Analysis Methods
Secondary endpoint: OS, starting from baseline in parent study.		
Secondary (FAS)	
OS time (in months) is defined as the date from baseline of parent study to the date of death due to any cause.
 
For participants alive at the time of data analysis or who are lost to follow-up, the OS will be censored at the date of data cut-off or date of last contact defined in Section 9.5.
 
OS (months) = (date of death/censoring – date of parent baseline + 1) / 30.4375
	
Date of death, with the reasons for censoring (alive, withdrawal of consent and lost to follow-up) will be presented in a participant listing.
 
OS will be estimated by the KM method. Median time to event will be reported, along with 25th and 75th percentiles.

The tumor evaluation data will be listed.

15 Safety Analyses

This section includes specifications for summarizing safety endpoints that are common across clinical studies such as adverse events, laboratory tests and vital signs.

Safety analyses will be done on the safety analysis set.

15.1 Primary Endpoint

15.1.1 Primary Objective: Analysis of the Primary Endpoint

Analysis (Analysis Set)	Derivation	Statistical Analysis Methods	Missing Data Handling
Primary endpoint: Occurrence of TEAEs and treatment-related TEAEs.			
Primary (SAF)	
TEAEs are those events with onset dates occurring during the on-treatment period for the first time, or if the worsening of an event is during the on-treatment period.
 
Treatment-related TEAEs are the adverse events with relationship to study treatment (as recorded on the "Adverse Events Details" eCRF page, Relationship with bintrafusp alfa = Related) reported by the investigator and those of unknown relationship (i.e. no answer to the question "Relationship with bintrafusp alfa").
	
The following frequency table will be prepared by primary SOC and PT in alphabetical order of SOC for:
 
• Any AE• Any related AE 
per indication or per parent protocol of the corresponding parent study.
 
The listings of all AEs will also be provided with the relevant information with a flag for AEs with onset outside of the on-treatment period.
	See Section 9.10

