2.3.3 Overall Benefit/Risk Conclusion

Participants enrolled in parent protocols with bintrafusp alfa treatment underwent benefit/risk assessments and, by means of their eligibility to participate in this rollover study, have an expected overall positive benefit from continuation or reinitiation of bintrafusp alfa treatment. Given the observed clinical activity of bintrafusp alfa in patients with a number of tumor types and the manageable safety profile observed in more than 700 participants in the Phase I and Phase II studies, the benefit/risk assessment is considered favorable to conduct this study.

3 Objectives and Endpoints

Table 3 Objectives and Endpoints

Objectives	Endpoints
Primary	
To evaluate clinical safety of bintrafusp alfa in participants with solid tumors who continue treatment after completion of the primary/main analyses in parent bintrafusp alfa studies	Occurrence of AEs and treatment-related AEs, starting from baseline in parent study
Secondary	
To evaluate clinical efficacy of bintrafusp alfa based on OS	OS, starting from baseline in parent study

AE = adverse event **CCI**; OS = overall survival **CCI**;

RECIST v1.1 = Response Evaluation Criteria in Solid Tumors Version 1.1.

4 Study Design

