8.2.4 Clinical Safety Laboratory Assessments

- Blood and urine samples will be collected for the clinical laboratory tests listed in [Appendix 6](#) at the time points listed in the SoA ([Table 1](#)). All samples will be clearly identified.

-
- Additional tests may be performed at any time during the study, as determined necessary by the Investigator or required by local regulations.
 - The tests will be performed by the local laboratory.

The Sponsor will receive a list of the local laboratory normal ranges before shipment of study intervention(s). Any changes to the ranges during the study will be forwarded to the Sponsor or designated organization.

The Investigator will review each laboratory report, document this review, and record any clinically relevant changes occurring during the study in the AE section of the CRF. The laboratory reports will be filed with the source documents.

8.3

Adverse Events and Serious Adverse Events

The definitions of an AE and a SAE are in [Appendix 4](#) Adverse Events: Definitions and Procedures for Recording, Evaluating, Follow-up and Reporting.

The Investigator and any qualified designees (e.g., Sub-Investigators) are responsible for detecting, documenting, and recording events that meet the definition of an AE or SAE. The Investigator remains responsible for following up AEs that are serious or that caused the participant to discontinue the study intervention as specified in [Section 8.3.3](#).

Requests for follow-up will usually be made via the Study Monitor, although in exceptional circumstances the global patient safety department may contact the Investigator directly to obtain further information or to discuss the event.

8.3.1

Time Period and Frequency for Collecting Adverse Event and Serious Adverse Event Information

- All AEs will be collected from the signing of the ICF until 90 days as specified in the SoA.
- All SAEs will be collected from the signing of the ICF until 90 days of last dose of the study treatment at the time points specified in the SoA ([Table 1](#)). Beyond this reporting period, any new unsolicited SAEs that the Investigator spontaneously reports to the Sponsor will be collected and processed.

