9.4.2 Safety Analyses

All safety analyses will be performed on the Safety Analysis population defined in the protocol of the respective parent study.

The on-treatment period is defined as the time from the first dose of study intervention administration in the parent study to the last study intervention administration date + 30 days or the earliest date of subsequent anticancer drug therapy minus 1 day, whichever occurs first, unless otherwise stated.

Safety endpoints include, but are not limited to, TEAEs, SAEs, treatment-related AEs, AESIs, irAEs, and IRRs, as well as clinical laboratory assessments, vital signs, and ECOG PS as described in [Section 8.2](#).

The definitions, procedures for recording, evaluating, Follow-up, and reporting of AEs are described in [Appendix 4](#).

TEAEs are those events with onset dates occurring during the on-treatment period or if the worsening of an event is during the on-treatment period. Severity of AEs will be graded using the version of CTCAE toxicity grades used in the respective parent study.

All premature terminations will be summarized by primary reason for treatment discontinuation/withdrawal.

As stated in the previous section, safety analyses will focus on the occurrence of new AEs that have not been reported in the parent studies to assess if they lead to changes in the safety assessment, as given in the clinical study report of the respective parent study.

Participants will be analyzed according to the actual treatment they receive. The specifics for analysis methods will be defined in the IAP and finalized before database lock.

Endpoint	Statistical Analysis Methods
Primary To evaluate clinical safety of bintrafusp alfa in participants with solid tumors who continue treatment after completion of the primary/main analyses in parent bintrafusp alfa studies.	The safety endpoints will be tabulated using descriptive statistics using MedDRA preferred terms and system organ class.
Secondary	Not applicable

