15.2 Adverse Events

Treatment-emergent adverse events (TEAE) are those events with onset or worsening (seriousness or severity) dates occurring within the on-treatment periods as defined in Section 9.7.

For immune-related AEs, an extended period of up to 90 days after last treatment is considered for analyses dedicated to irAEs. PTs belonging to irAEs will be considered as treatment-emergent up to 90 days for dedicated irAE analyses and up to 30 days for general AE analyses.

This includes also AEs ongoing at baseline, which first improve under study intervention and then worsen irrespective of baseline. Adverse events with changes in toxicity grade/severity, seriousness or outcome of AEs are recorded as separate entries in the eCRF with associated end and start dates. Records of the same AE will be considered as one event in the analysis. If the severity of the reported event worsens after start of treatment, the TEAE flag will be re-evaluated for the worse and the subsequent records as per the TEAE definition. If the worse record starts outside of the on-treatment period, it will not appear on the summaries/listings of TEAEs, unless otherwise specified. These events will be kept as separate records in the database in order to maintain the full detailed history of the events. The overall outcome of the adverse event is the

outcome of the last event in the sequence. When such AEs are listed, start, end date and outcome should be provided together with change date, toxicity grade/severity and seriousness per episode.

Adverse events related to study intervention are those events with relationship missing, unknown or yes.

Immune-Related Adverse Events (irAE) are identified according to the methodology outlined in Appendix 1 for a pre-specified search list of MedDRA PTs, documented in the Benefit Risk Strategy Document. Prior to DB lock these events are identified according to a pre-specified search list of MedDRA PTs, documented in a version-controlled repository maintained by the Sponsor and based on medical assessment prior to analysis of the current study. Details are included in Appendix 1.

Infusion-Related Reactions (IRR) are identified based on a list of MedDRA PTs. The detailed criteria of the timing relationship to infusions are specified in [Table 1](#) of Appendix 1.

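### SAP 15.1.1 narrows the primary endpoint from AEs to TEAEs; on that reading, AEs first starting 31–90 days after last dose are collected but left out of the primary tables

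*SAP*

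**What the plan says.** Protocol Section 3 (Table 3) gives the primary endpoint as "Occurrence of AEs and treatment-related AEs, starting from baseline in parent study". The objectives table in SAP Section 5 uses the same words.

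SAP 15.1.1 heads its analysis row "Primary endpoint: Occurrence of TEAEs and treatment-related TEAEs". Its derivation cell says "TEAEs are those events with onset dates occurring during the on-treatment period for the first time", and also admits events that worsen in that period. The methods cell of the same row labels the frequency tables *Any AE* and *Any related AE*.

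Protocol 9.4.2 ends the on-treatment period at the earlier of "last study intervention administration date + 30 days or the earliest date of subsequent anticancer drug therapy minus 1 day". SAP 15.2 agrees on the general limit: immune-related preferred terms are "considered as treatment-emergent up to 90 days for dedicated irAE analyses and up to 30 days for general AE analyses".

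On collection, Protocol 8.3.1 states "All AEs will be collected from the signing of the ICF until 90 days as specified in the SoA". The synopsis and the Schedule of Activities count the 90 days from last dose.

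Protocol 9.4.2 also states: "Safety endpoints include, but are not limited to, TEAEs, SAEs, treatment-related AEs, AESIs, irAEs, and IRRs". TEAEs and treatment-related AEs are separate items in that list.

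**The concern.** The stated endpoint carries no treatment-emergent restriction; the analysed one does. The restriction is least easily justified for related events. A TEAE window usually serves to set aside events unlikely to be caused by the drug. Here the investigator has already assessed causality (Protocol Appendix 4), so the window can remove events judged related to bintrafusp alfa. The SAP itself treats days 31–90 as relevant for irAEs, but only in the dedicated irAE tables.

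At stake is whether the primary safety tables describe all the safety data that the protocol collects. A programmer also cannot satisfy Section 5, the endpoint line, the derivation cell and the table labels of 15.1.1 all at once.

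**Working it through.** The plan gives no figure to reproduce. The study is single-arm and descriptive, so the check compares the windows and then follows a late event through the outputs.

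**Window.** Inputs: AE collection to day 90 after last dose (Protocol 8.3.1, synopsis, Schedule of Activities); general TEAE cut-off at day 30 (Protocol 9.4.2, SAP 15.2).

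- Days collected but outside the window: 90 − 30 = 60.
- Share of post-dose collection time: 60 / 90 = 66.7%.
- The gap opens before day 31 for a participant who starts new anticancer drug therapy earlier.

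This is a share of calendar time, not of events.

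**Where an AE with first onset on, say, day 45 appears, reading 15.1.1 as TEAEs**

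| Output | Is it counted? |
|---|---|
| Primary SOC/PT tables (SAP 15.1.1) | No |
| Related rows of the overall summary (15.2.1) | No |
| Rollover repeats of those tables (15.2, 15.2.1) | No; 15.2 defines these events as TEAEs |
| irAE table (15.3.3) | Yes, if immune-related |
| Anemia and bleeding tables (15.3.3) | Specified as TEAEs; no 90-day extension stated |
| Deaths table (15.3.1) | Yes, if the participant dies; treatment-related is one of the reasons |
| Rollover SAE table (15.3.2) | Possibly, if serious; not split by relationship |
| AE listings (15.1.1, 15.2) | Yes, flagged as outside the on-treatment period |

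**Direction.** Extending the window to day 90 adds events and leaves the denominator unchanged. The number of participants in each row can therefore only stay the same or rise.

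**Size.** The documents give no onset rates. Purely as an illustration, take N = 10 (the protocol expects at least 10 participants) and let p be an assumed chance per participant of a new related AE on days 31–90. The chance that at least one participant has such an event is 1 − (1 − p)^10:

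| Assumed p | At least one of 10 |
|---|---|
| 5% | 40.1% |
| 10% | 65.1% |
| 20% | 89.3% |
| 30% | 97.2% |

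A row changes only if that participant is not already counted in it. In that case one participant moves a row based on 10 people by 1/10 = 10 percentage points. The tables are by indication or parent protocol, so the actual denominators will differ from 10.

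**The case against.** The strongest defence is that the protocol supports TEAE summaries. Section 9.4.2 defines the on-treatment period and TEAEs, names TEAEs among the safety endpoints, and leaves the specifics of method to the analysis plan. The endpoint wording fixes a start (parent baseline) but no end. This justifies keeping the 30-day tables. It does not make them the stated primary endpoint, because neither Table 3 nor the treatment-related AE item in 9.4.2 carries the restriction.

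A second defence is that the labels *Any AE* and *Any related AE* may be meant literally, since the default to TEAEs in SAP 15.2 is stated for that section and not for 15.1.1. This ambiguity is real. The endpoint line and derivation cell favour the TEAE reading, as does the contrast with the listings of all AEs. If the labels are what was intended, those two cells need correcting.

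A reader might infer that late related events, including fatal and serious ones, survive only in listings. The documents do not support that. SAP 15.3.1 tabulates all deaths with a treatment-related reason, and 15.3.2 presents SAEs during the Rollover study alongside on-treatment SAEs. The most serious late events are the best covered.

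Nor can it be said that the SAP fails to declare the change. The visible part of Section 7 mentions only COVID-19 subsections and analysis timing, but part of it is redacted. SAP Section 9.7, to which 15.2 refers for the on-treatment periods, is not visible either, so the 30-day limit rests on Protocol 9.4.2 and SAP 15.2.

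**Conclusion.** The mismatch stands. SAP 15.1.1 departs from Protocol Table 3 and from SAP Section 5, and is inconsistent within its own row. On the TEAE reading, first onsets on days 31–90 after last dose are absent from the primary tables and from the related rows of the 15.2.1 summary. This affects both halves of the endpoint, all AEs as well as related AEs.

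The size is unknown. It is tempting to conclude that two thirds of post-treatment related AEs are lost, or that the primary result is certainly too favourable. The first would require even onset over 90 days, which nothing in the documents shows, and it would ignore the related AEs already counted since parent baseline. For the second, the documents support only that the tables are equal to or more favourable than tables of all collected events. The rows most open to change are single preferred terms, Grade ≥3 and serious events, where a participant is less likely to be counted already.

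The point merits correction because it concerns the primary endpoint and the data will already be in hand. It does not show that safety data are lost.

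**What to change.** In SAP 15.1.1, produce the *Any AE* and *Any related AE* SOC/PT tables on all AEs from first dose to 90 days after last dose, and do the same for the related rows of the 15.2.1 overall summary. Keep the 30-day TEAE tables beside them. Make the endpoint line, derivation cell and table labels agree with Section 5.

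If the endpoint is to stay TEAE-only, declare this in SAP Section 7, unless the redacted part already does so, and align Section 5 and the labels.

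The cost is SAP wording and one extra run of existing tables on collected data. Counts may become slightly less favourable, and some added events will have started after new anticancer therapy, which makes attribution harder. Showing the 30-day tables alongside lets the reader see that difference.

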15.2 Adverse Events

Treatment-emergent adverse events (TEAE) are those events with onset or worsening (seriousness or severity) dates occurring within the on-treatment periods as defined in Section 9.7.

For immune-related AEs, an extended period of up to 90 days after last treatment is considered for analyses dedicated to irAEs. PTs belonging to irAEs will be considered as treatment-emergent up to 90 days for dedicated irAE analyses and up to 30 days for general AE analyses.

This includes also AEs ongoing at baseline, which first improve under study intervention and then worsen irrespective of baseline. Adverse events with changes in toxicity grade/severity, seriousness or outcome of AEs are recorded as separate entries in the eCRF with associated end and start dates. Records of the same AE will be considered as one event in the analysis. If the severity of the reported event worsens after start of treatment, the TEAE flag will be re-evaluated for the worse and the subsequent records as per the TEAE definition. If the worse record starts outside of the on-treatment period, it will not appear on the summaries/listings of TEAEs, unless otherwise specified. These events will be kept as separate records in the database in order to maintain the full detailed history of the events. The overall outcome of the adverse event is the

outcome of the last event in the sequence. When such AEs are listed, start, end date and outcome should be provided together with change date, toxicity grade/severity and seriousness per episode.

Adverse events related to study intervention are those events with relationship missing, unknown or yes.

Immune-Related Adverse Events (irAE) are identified according to the methodology outlined in Appendix 1 for a pre-specified search list of MedDRA PTs, documented in the Benefit Risk Strategy Document. Prior to DB lock these events are identified according to a pre-specified search list of MedDRA PTs, documented in a version-controlled repository maintained by the Sponsor and based on medical assessment prior to analysis of the current study. Details are included in Appendix 1.

Infusion-Related Reactions (IRR) are identified based on a list of MedDRA PTs. The detailed criteria of the timing relationship to infusions are specified in [Table 1](#) of Appendix 1.

All analyses described in Section 15.2 will be based on TEAEs if not otherwise specified. The AE listings will include all AEs (whether treatment-emergent or not). AEs outside the on-treatment period will be flagged in the listings.

In addition, selected analyses will be repeated for the TEAEs that occurred during the Rollover study. TEAEs occurring during the Rollover study are defined as TEAEs with onset or worsening (seriousness or severity) date after the first dose of study intervention in the Rollover study.

Unless otherwise specified, TEAEs will be summarized by number and percentage of participants with the TEAE by primary SOC and PT in the category of interest in alphabetical order, per indication or per parent protocol of the parent study.

Each participant will be counted only once within each SOC or PT. If a participant experiences more than one AE within a SOC or PT for the same summary period, only the AE with the strongest relationship or the worst severity, as appropriate, will be included in the summaries of relationship and severity.

